3 STUDY OBJECTIVES

3.1 Primary Objective

The primary objective of this study is to assess the **safety** and **tolerability** of ABI-009 over a range of doses and to determine the DLT and MTD in participants with surgically-refractory epilepsy.

Safety: Defined as the incidence of AEs and SAEs during the study period. We will assess adverse events according to the National Cancer Institute Common Toxicity Criteria for Adverse Events version 4.03. MTD will be determined based on safety assessment, including the Columbia-Suicide Severity Rating Scale (C-SSRS) which will be administered at baseline, after study drug, and during follow-up.

Tolerability: Defined as the rate of withdrawal from the study, either voluntary or as medically directed as well as rate of compliance with medication regimen.

Columbia-Suicide Severity Rating Scale (C-SSRS) serious suicidal ideation score stays below a 4

3.2 Secondary Objectives

The secondary objectives of this study are to:

- Determine **efficacy**. Efficacy is defined as the change in seizure frequency between baseline and follow-up, expressed as **percentage reduction in seizure rate** (reduction in seizure frequency from baseline, calculated as (Baseline frequency [seizures/month] – frequency at follow-up [seizures/month])/Baseline frequency [seizures/month]) and **median percentage reduction** in seizure frequency. **Treatment response rate** will be defined as the proportion of participants achieving at least a 25% reduction in seizure frequency from baseline. **Seizure frequency** will be defined as the ratio between the number of seizures and the number of days on which seizure information was known within the same period of time (for either baseline or maintenance phase). Additional secondary endpoints will include **frequency of seizure-free days** during the maintenance period, **seizure-free rate** (participants remaining seizure free during the maintenance period), and rapamycin **blood level-response relationship** analysis.
- Determine **quality of life** and **behavioral** changes. Quality of Life for Children with Epilepsy Parent Form (QOLCE) [1] and Nisonger Child Behavioral Rating Form (NCBRF) [2, 3] will be completed at baseline, at the completion of maintenance, and at the completion of the 3 month follow-up period.
- Determine weekly whole blood rapamycin trough levels for three consecutive weeks.

3.3 Exploratory Objectives

For children enrolled in the study who underwent epilepsy surgery at our institution, informed consent will be sought for us to use their previously acquired/banked surgical tissue (including fibroblast cultures) for the following exploratory aims:

- To explore associations between histopathologic diagnosis and seizure outcomes
- To explore associations between pS6 positivity and seizure outcomes
- To analyze key molecular features including activation of the PI3K, mTOR and MAPK pathways as they relate to seizure outcomes
- To possibly perform additional genomic studies or obtain previously performed genomic analyses including genomic profiling from peripheral samples and correlate to seizure outcomes
- Explore any relationships between safety, efficacy and whole blood rapamycin trough levels
- Explore any relationships between AED levels (acquired outside the study through clinical standard of care) and rapamycin levels during the study

None of the exploratory aims would require additional experimental procedures to the participants throughout the study beyond those explicitly discussed in the protocol. Tissue would only be tested on participants who have already consented to and have banked tissue within our institution from prior epilepsy-related procedures.

4 STUDY DESIGN

4.1 Study Overview

This is a prospective, single-center, non-randomized open-label phase 1 study to investigate multiple dose levels of ABI-009 for surgically-refractory epilepsy. Up to 18 participants are planned to be enrolled into the study.

The duration of participation for each participant is up to 18 weeks, including a 4-week baseline period to obtain baseline outcome rates, a 3-week active study period and a 12-week follow-up period (see Figure 1). After the baseline period, participants will be started on the assigned dose of ABI-009, given once weekly for a total of 3 weeks. Dose levels to be tested are below:

For dose finding, ABI-009 will be tested in cohorts of 3 participants each using the standard 3+3 dose-finding design. Initial starting dose will be at 5 mg/m²/week.

Table 3: ABI-009 Cohort Dosing Schedule

Dose levels	ABI-009 in mg/m ²
-2	1
-1	2.5
1	5
2	10

3	20
---	----

Escalation to the next dose level with a new cohort of 3 participants will occur after no DLT was observed. There will be no intra-participant dose escalation allowed. If a DLT occurs in a cohort, an additional 3 participants will be recruited to the cohort. If no further DLTs occur, then a new cohort of 3 participants at the next higher dose level can be enrolled. If 2/6 participants at a dose level experience a DLT, then the cohort will be closed to further enrollment and 3 participants will be enrolled at the next lower dose level, and so on. The MTD is the highest dose level in which ≤ 1 participant has a DLT. There will be no intra-participant dose escalation allowed.

Once the MTD has been determined, the MTD cohort will be opened for an estimated additional 6 participants. These participants will adhere to the identical protocol of the rest of their cohort.

Product will be administered IV every 7 days for 3 weeks.

For a detailed review of visits, please see Appendix 1.

Total duration of the study is expected to be about one year.

5 CRITERIA FOR EVALUATION

5.1 Primary Endpoints

I. Safety

- DLT and MTD
- Incidence of adverse events and clinically significant abnormal lab values during dosing

II. Tolerability

- Voluntary or medically-determined withdrawal from study
- Adherence to medication regimen
- C-SSRS serious suicidal ideation score stays below a 4 rating

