	
[seizures/week])/Baseline frequency [seizures/week]) and median percentage reduction in seizure frequency. Treatment response rate will be defined as the proportion of participants achieving at least a 25% reduction in seizure frequency from baseline. Seizure frequency will be defined as the ratio between the number of seizures and the number of days on which seizure information was known within the same period of time (for either baseline or maintenance phase). Additional secondary endpoints will include frequency of seizure-free days during the maintenance period, seizure-free rate (participants remaining seizure free during the maintenance period), and rapamycin blood level-response relationship analysis. These endpoints will be analyzed using appropriate statistical tests, such as the test of proportions and time to event analyses.
 
Quality of Life for Children with Epilepsy Parent Form (QOLCE) [1] and Nisonger Child Behavioral Rating Form (NCBRF) [2, 3] scores will be compared using appropriate statistical tests for ordinal data, including Wilcoxon signed rank tests, logistic regression, or contingency tables.

Rationale for Number of Participants	In this phase 1 study, it is estimated that a maximum of up to 18 participants will be required to achieve the MTD; however, MTD could be reached with as few as 9 participants, but also possible that the MTD is not reached in this study. With the MTD expansion cohort, it is estimated that additional 6 participants would bring the maximum number of participants enrolled to 18. A total of up to 18 participants should be enough for a safety and tolerability study in an orphan condition.

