9.1.13 Columbia-Suicide Severity Rating Scale (C-SSRS)

The C-SSRS is a suicidal ideation and behavior rating scale to identify risk in participants. The questionnaire will be given at the end of the 1-month baseline phase, at the end of the 3-week treatment phase, and again at the end of the 3-month follow-up period. Participant serious suicidal ideation scores must remain below a 4 in order to stay on study.

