12 DISCONTINUATION AND REPLACEMENT OF PARTICIPANTS

12.1 Early Permanent Discontinuation of ABI-009 Dosing

A participant may be permanently discontinued from ABI-009 dosing at any time if the participant, the investigator, or the Sponsor feels that it is not in the participant's best interest to continue. The following is a list of possible reasons for early permanent discontinuation of study treatment:

- Participant or participant's legal representative decision
- Protocol violation
- C-SSRS serious suicidal ideation score is increased to a 4 rating
- Death
- Pregnancy
- Refusal to complete patient diary, QOLCE, NCBRF, or C-SSRS questionnaires

If a participant is permanently discontinued from dosing early due to an adverse event, the participant will be followed and treated by the Investigator until the abnormal parameter or symptom has resolved or stabilized.

All participants who permanently discontinue study dosing early should come in for an early permanent discontinuation of study treatment visit as soon as possible and complete all remaining scheduled visits and procedures.

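### The primary C-SSRS endpoint uses only the ideation score, so suicidal behaviour recorded on the same form leaves it satisfied, and section 15 plans no C-SSRS summary

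*Combined protocol and SAP*

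**What the plan says.** The criterion "C-SSRS serious suicidal ideation score stays below a 4 rating" stands under Tolerability in section 5.1, beside withdrawal and adherence. The synopsis (primary objective and primary endpoint) and section 3.1 repeat it in substance.

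Section 9.1.13 describes the instrument: "The C-SSRS is a suicidal ideation and behavior rating scale to identify risk in participants". On timing it says: "The questionnaire will be given at the end of the 1-month baseline phase, at the end of the 3-week treatment phase". A third administration is planned when follow-up closes. Sections 10.3, 10.5, 10.6 and 10.7 and the Schedule of Events place the form at Visit 2, Visit 6, Visit 9 and the early-discontinuation visit.

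The same threshold has two other uses. Section 9.1.13 makes it a condition for each participant: "Participant serious suicidal ideation scores must remain below a 4 in order to stay on study". Section 12.1 lists among possible reasons for ending dosing: "C-SSRS serious suicidal ideation score is increased to a 4 rating".

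Section 3.1 also ties the scale to dose finding: "MTD will be determined based on safety assessment, including the Columbia-Suicide Severity Rating Scale (C-SSRS". The rule in section 4.1 is: "The MTD is the highest dose level in which ≤ 1 participant has a DLT". Neither that rule nor the DLT definition in section 8.5 mentions the C-SSRS.

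Section 15.3 covers AEs, SAEs, laboratory data and hospitalisation. Section 15.4 covers drug discontinuation and infusion compliance. Section 15.5 covers seizure outcomes, QOLCE and NCBRF. None mentions the C-SSRS.

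**The concern.** As written, the endpoint has one input, the ideation score, and one cut, at 4. Behaviour that the form records does not enter. The report could therefore state that the primary suicidality criterion was satisfied for a participant whose own form recorded suicidal behaviour. A participant who goes from no ideation at the drug-free Visit 2 to a score of 3 after dosing also satisfies it, with nothing planned to display the change.

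The protocol states the criterion for the individual and does not say how it becomes a result for a dose level or for the trial. With no summary in section 15, that choice would be made after the data are known. At stake is how a primary safety statement in a small, mainly paediatric phase 1 study would be read.

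**Working it through.** **1. What the endpoint can see.** This follows from the wording and needs no assumed rate.

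| Recorded on the form after dosing | Ideation score | Criterion in section 5.1 |
|---|---|---|
| No behaviour | 3 or less | satisfied |
| Suicidal behaviour | 3 or less | satisfied |
| Either | 4 or more | not satisfied |

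The second row is the gap. The synopsis, sections 3.1 and 5.1, the stay-on-study sentence in 9.1.13 and the list in 12.1 all refer to the ideation score alone.

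**2. What other reporting can see.** AEs are collected from enrolment to the end of participation (sections 9.1.14 and 11.1). Serious events are SAEs (section 11.2), and AE summaries go to the DSMB (section 14). A DLT requires grade 3 or higher and a definite or probable attribution (section 8.5). Section 11.1 also allows the attribution possible, so an event rated that way would not be a DLT. Other routes therefore exist, but none of them changes the second row of the table.

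**3. Is there a plan figure to reproduce?** No. The documents give no acceptable event rate, error rate or confidence bound for the C-SSRS. The only related figure is the sample size. The synopsis says "A total of up to 18 participants should be enough for a safety and tolerability study in an orphan condition", and section 15.6 bases the number on feasibility and the 3+3 scheme.

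**4. What zero events would leave open.**

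- A dose level has 3 participants, or 6 after one DLT, and the MTD expansion adds an estimated 6 (section 4.1). The MTD group is then 3 + 6 = 9 or 6 + 6 = 12. The stated maximum over all doses is 18.
- For 0 events in n, the exact one-sided 95% upper bound is 1 − 0.05^(1/n). The upper limit of the two-sided 95% Clopper-Pearson interval is 1 − 0.025^(1/n).

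| Events/n | One-sided 95% bound | Two-sided 95% upper limit |
|---|---|---|
| 0/9 | 1 − 0.05^(1/9) = 28.3% | 33.6% |
| 0/12 | 1 − 0.05^(1/12) = 22.1% | 26.5% |
| 0/18 | 1 − 0.05^(1/18) = 15.3% | 18.5% |

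These assume that every dosed participant has at least one form after dosing. If the expansion did not take place and the MTD group stayed at 6, the one-sided bound for 0/6 would be 1 − 0.05^(1/6) = 39.3%.

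**The case against.** The strongest reply is that suicidal behaviour is already covered by other primary endpoints. AE incidence is one of them, and section 15.3 tabulates AEs by seriousness, severity and relationship. A related event of grade 3 or higher feeds the MTD rule as a DLT, and the DSMB sees all AEs before each escalation cohort and before the expansion. This stands as a limit on the harm: one line of a multi-part primary endpoint is too narrow, and the trial is not blind to the event. It does not correct that line, which would still read as satisfied beside the AE.

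A second reply is that section 15.1 leaves detailed analyses to a later SAP, and that wide bounds follow for any rare event in a study of this size. This also stands in part. The missing confidence limit alone is missing detail. But the ideation-only definition is in section 5.1, and an analysis plan that follows it will inherit it.

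A third reply is that the cut of 4 is used consistently, so objecting to a change from 0 to 3 is a matter of preference. Agreed. The cut is not challenged here, and a shift table would only describe such changes.

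A reader might go further and infer that the trial passes whenever nobody reaches 4, and that a relevant harm would therefore usually pass at the MTD. The documents do not support this. They contain no group pass rule, since section 9.1.13 speaks of the individual participant, and they define no relevant rate. Even under a zero-event rule the inference depends on the assumed rate. The chance of no score of 4 or more is 0.95^9 = 63% or 0.95^12 = 54% at an assumed 5%, but 0.90^9 = 39% or 0.90^12 = 28% at 10%. Nor is it informative that behaviour-only events always satisfy the criterion. That is true by construction, and the documents do not show how often behaviour occurs without a high ideation score.

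**Conclusion.** The point holds in a limited form. The primary C-SSRS endpoint leaves out the behaviour part of a scale that the protocol itself describes as covering behaviour, and no C-SSRS summary is planned. The omission is a matter of definition and rests on no assumed rate. Its practical size cannot be estimated, because the documents give no frequency for behaviour with an ideation score of 3 or less.

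The precision figures rest on an MTD group of 9 or 12 and complete forms. Zero events would leave true rates up to about 22% to 28% at the MTD, and 15% over 18 participants, not excluded at one-sided 95%. These figures show how a zero should be reported and are not evidence that harm is likely.

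Two inconsistencies belong with this point. Section 3.1 says that the MTD assessment includes the C-SSRS, but sections 4.1 and 8.5 give it no role. Section 9.1.13 makes the score a condition for staying on study, whereas section 12.1 lists it as a possible reason for ending dosing and then expects the remaining visits to be completed. Overall this is a cheap improvement to a primary safety statement, not a flaw that undermines the trial.

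**What to change.** - In section 5.1, the synopsis and section 15, define the endpoint as the number and proportion of dosed participants with, at Visit 6, Visit 9 or the early-discontinuation visit, an ideation score of 4 or more or any recorded suicidal behaviour.
- Report it by dose level, at the MTD and overall, with an exact confidence limit. State whether the limit is one-sided or two-sided, and how participants with no form after dosing are counted.
- Tabulate the shift in ideation score from Visit 2.
- If no events occur, report that none was observed and give the rate not excluded for the actual denominator.
- Reconcile section 3.1 with sections 4.1 and 8.5 on whether the C-SSRS affects the MTD. Reconcile the endpoint with the stay-on-study and discontinuation text in 9.1.13 and 12.1. How those clinical rules should read is for the sponsor to decide.

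The cost is wording in three places and a small set of tables. The form is already given at every visit needed, so no visit or procedure is added. The downside is that the endpoint may be met less often and the safety statement becomes somewhat less favourable.

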5.2 Secondary Endpoints

I. Efficacy

- Seizure frequency
- Percentage reduction in seizure frequency
- Median percentage reduction in seizure frequency
- Response rate
- Frequency of seizure-free days
- Seizure-free rate
- Rapamycin blood level–response relationship

II. Quality of life and behavioral changes

- Quality of Life for Children with Epilepsy Parent Form (QOLCE) [1] and

- Nisonger Child Behavioral Rating Form (NCBRF) [2,3]
- Both will be completed at baseline, at the completion of maintenance, and at the completion of the 3-month follow-up period.

III. Weekly whole blood rapamycin trough levels for three consecutive weeks.

6 PARTICIPANT SELECTION

6.1 Study Population

Participants with a diagnosis of medically intractable epilepsy who meet all of the inclusion and none of the exclusion criteria will be eligible for participation in this study. Participants must be enrolled before study procedures begin.

6.2 Inclusion Criteria

1. Written informed consent (and assent when applicable) obtained from participant or participant's legal representative
2. Be willing and able to adhere to the study visit schedule and other protocol requirements
3. Male or female ≥ 3 and ≤ 26 years of age at Visit 1
 - b. Because no dosing or adverse event data are currently available on the use of ABI-009 or other mTOR inhibitors in participants <3 years of age, these young children are excluded from this study.
4. Documentation of a diagnosis of medically intractable epilepsy as defined by the failure of at least 2 appropriately dosed and tolerated AEDs to eliminate all clinical seizures over a 6-month period, prior to epilepsy surgery
5. Documentation of resective epilepsy surgery following appropriate pre-surgical evaluation
6. Documentation of continued clinical seizures that persist at least 3 months following resective epilepsy surgery. In order to proceed with enrollment and study drug initiation, participants will have to have had >8 seizures in the last 30 days without 2 consecutive weeks of seizure freedom, as noted by a daily seizure diary.
7. Documentation that the participant is not a candidate for *or* refuses any additional resective epilepsy surgery
8. Participants must have adequate bone marrow function (ANC $\geq 1,000/\text{mm}^3$, platelet count of $\geq 100,000/\text{mm}^3$, and hemoglobin $\geq 9 \text{ gm/dL}$) before study drug dosing.
9. Participants must have adequate liver function (SGPT/ALT ≤ 5 times ULN and bilirubin ≤ 5 times ULN) before study drug dosing.
10. Participants must have adequate renal function, defined as: Creatinine clearance or radioisotope GFR $\geq 70\text{mL/min}/1.73 \text{ m}^2$ **or** a serum creatinine before study drug dosing based on age/gender as follows:

Age	Maximum Serum Creatinine (mg/dL)	
	Male	Female
3 to < 6 years	0.8	0.8
6 to < 10 years	1	1
10 to < 13 years	1.2	1.2
13 to < 16 years	1.5	1.4
≥ 16 years	1.7	1.4

The threshold creatinine values in this table were derived from the Schwartz formula for estimating GFR utilizing child length and stature data published by the CDC.

11. Participants must have a fasting cholesterol level <350 mg/dL and triglycerides <400 mg/dL before starting study drug. In case one or both of these are exceeded, the participant can only be included after initiation of appropriate lipid lowering medication and documentation of cholesterol <350mg/dL and triglycerides <400mg/dl before study drug dosing.
12. Participants must have normal oxygen saturation before study drug dosing.
13. The effects of ABI-009 on the developing human fetus at the recommended therapeutic dose are unknown. For this reason and because rapamycin is known to be teratogenic, female participants of child-bearing potential and men must agree to use adequate contraception (hormonal or barrier method of birth control; abstinence) prior to study entry and for the duration of study participation. Should a female participant become pregnant or suspect she is pregnant while participating in this study, she should inform her treating physician immediately.
 - a. Participants of child bearing potential must not be breastfeeding or pregnant as evidenced by a negative pregnancy test at enrollment and before study drug initiation.

6.3 Exclusion Criteria

1. For females of child bearing potential:
 - a. Positive pregnancy test at Visit 1, or
 - b. Lactating, or
 - c. Unwilling to practice a medically acceptable form of contraception (acceptable forms of contraception: abstinence, hormonal birth control, intrauterine device, or barrier method plus a spermicidal agent), unless surgically sterilized or postmenopausal during the study.
2. Participant has any other condition that, in the opinion of the Site Investigator/designee, would preclude informed consent or assent, make study participation unsafe, complicate interpretation of study outcome data, or otherwise interfere with achieving the study objectives.
3. Participants has received immunization with attenuated live vaccines within one week of study entry and/or is planning to receive immunization with attenuated live vaccines during study period. Examples of live vaccines include intranasal influenza, measles, mumps, rubella, oral polio, BCG, yellow fever, varicella and TY21a typhoid vaccines. Close contact

with those who have received attenuated live vaccines should be avoided during the ABI-009 dosing period.

4. Participant tests positive for Hepatitis C antibodies or the Hepatitis B antigen. HBsAg and HCVAb blood test must be done at screening (HBsAg only needs to be screened in patients who have not received the full complement of Hepatitis B immunizations). Alternatively, if the patient has received the complement of Hepatitis B immunizations and documentation is provided, this would suffice.
5. A known history of HIV seropositivity. HIV-positive patients on combination antiretroviral therapy are ineligible because of the potential for pharmacokinetic interactions with ABI-009. In addition, these patients are at increased risk of lethal infections when treated with marrow-suppressive therapy.
6. Participant is receiving chronic, systemic treatment with corticosteroids or another immunosuppressive agent. Note: Patients that are currently using inhaled, intranasal, ocular, topical or other non-oral or non-IV steroids are not necessarily excluded from the study but must be discussed with the study chair.
7. Participant has been previously treated with a systemic mTOR inhibitor for epilepsy. Skin cream use with rapamycin or everolimus, however, is permitted.
8. Participant has a known hypersensitivity to human albumin, ABI-009 or other rapamycins (e.g. sirolimus, everolimus, temsirolimus).
9. Participant is receiving any other concurrent anticancer or investigational therapy. Participants will be permitted to enroll in the study after a 30-day washout of previously used investigational drugs.
10. Participant has any clinically significant unrelated systemic illness that would compromise a participant's ability to tolerate protocol procedures.
11. Participant is unable to return for dosing and follow-up visits to assess toxicity to the study drug.
12. Participant has uncontrolled intercurrent illness including, but not limited to, ongoing or active infection, symptomatic congestive heart failure, unstable angina pectoris, cardiac arrhythmia, active lung disease, or psychiatric illness/social situations that would limit compliance with study requirements. Study Specific Tolerance for Inclusion/Exclusion Criteria

Patients who fail to meet one or more of the inclusion criteria or who meet any of the exclusion criteria will not be enrolled in this study. Waivers of any of the above study entry criteria will not be granted.

